8.3. Study cohorts to be evaluated

8.3.1. Total cohort

The Total cohort will include all subjects enrolled in the study.

8.3.2. According-To-Protocol cohort

The ATP cohort will include all evaluable subjects, that is, subjects who meet all eligibility criteria, complying with the procedures defined in the protocol and for whom data of at least one follow-up contact are available. The surveillance period for one subject will be defined as the duration from date of enrolment until the date of the last follow-up contact for this subject. Reasons for elimination from ATP analyses will be established at the time of data cleaning and documented.

8.4. Conduct of analyses

Any deviation(s) or change(s) from the original statistical plan outlined in this protocol will be described and justified in the final study report.

8.4.1. Sequence of analyses

An interim analysis will be performed when subjects from the initial cohort of first two sites have completed two years of surveillance (Visit 4) and the third site have completed at least one year of surveillance (Visit 3). All analyses of primary and secondary objectives will be performed on data as cleaned as possible.

The final analysis will be performed when all prospective data have been collected and cleaned.

8.5. Statistical methods

Any deviation or change from the original statistical plan will be described and justified in the final study report.

All the analyses of primary objectives will be performed on the ATP cohort. Analysis of demographics will be performed on the total cohort.

8.5.1. Analysis of demographics/baseline characteristics

Socio-demographic and patient characteristics (e.g., age at study enrolment, gender, household conditions, medical history and vaccination history) will be summarized overall and by region, and at the beginning of each season using descriptive statistics.

8.5.2. Analysis of primary and secondary endpoints

The following analyses will be performed overall and by DENV type, study site, gender and age-group previous dengue exposure (Yes = DENV IgG antibodies at previous visit and No = no DENV IgG antibodies at previous visit):

- Incidence rate of laboratory-confirmed symptomatic dengue infection with 95% CI for each season separately: the numerator will be the number of subjects with lab-confirmed symptomatic dengue infection during the season (between the visits scheduled before and after the season). The denominator will be the total person-years at risk, i.e. from the visit scheduled before the season until the first RT-qPCR confirmed symptomatic dengue infection during the season, the next scheduled visit or the subject's withdrawal, whichever comes first.
- Incidence rate of laboratory-confirmed symptomatic dengue infection with 95% CI all seasons combined: the numerator will be the number of subjects with lab-confirmed symptomatic dengue infection during the study period. The denominator will be the total person-years at risk, i.e. from enrolment until the first RT-qPCR confirmed symptomatic dengue infection, the end of the study or the subject's withdrawal, whichever comes first.

The following analyses will be performed by study site, gender and age-group previous dengue exposure (primary or secondary):

- Incidence rate of laboratory confirmed or probable symptomatic dengue infections with 95% CI for each season separately and overall. The numerator will be the number of subjects with symptomatic dengue infection (including laboratory-confirmed and probable cases) during the period. The denominator will be the total person-years at risk.
- Incidence rate of probable symptomatic dengue infection with 95% CI for each season separately and overall. The numerator will be the number of subjects with probable symptomatic dengue infection. The denominator will be the total person-years at risk.

The following analyses will be performed by study site, gender and age-group:

- The proportion of subjects with primary inapparent dengue infection at each subsequent scheduled visit (not at enrolment) with 95% CI will be calculated as the number of dengue IgG positive cases and at the visit divided by the total number of subjects IgG negative at the previous visit.
- The proportion of subjects with secondary symptomatic dengue infection (probable or confirmed) at each subsequent scheduled visit (not at enrolment) with 95% CI will be calculated as the number of subjects with secondary symptomatic infection since the previous visit divided by the total number of IgG positive subjects at the previous visit.

- The (crude) seroprevalence of dengue infection will be calculated at enrolment and at each scheduled visit as a proportion (i.e., the number of dengue IgG positive subjects tested positive at this visit or known to be positive from previous visits divided by the total number of subjects for whom dengue IgG serostatus is known).
- The clinical characteristics of symptomatic dengue infection (symptoms, hospitalizations, severity) will be presented as proportions of dengue cases overall and per sub-group (type (DENV 1-4), study site, gender and age group).

Endpoint numerators and denominators are described in [Table 16](#) below:

Table 16 Numerators and Denominators within each strata (DENV type, study site, gender and age-group and previous dengue exposure (primary or secondary))

Analysis	Numerator	Denominator
Incidence rate of laboratory confirmed symptomatic infection by year	All confirmed acute cases during the season (between the visits scheduled before and after the season)	Total person-years at risk, i.e. from the visit scheduled before the season until the first RT-qPCR confirmed symptomatic dengue infection during the season, the next scheduled visit or withdrawal, whichever comes first.
Incidence rate of laboratory-confirmed symptomatic dengue infection for all seasons combined	All confirmed acute cases during the study period	Total person-years at risk, i.e. from enrolment until the first RT-qPCR confirmed symptomatic dengue infection, the end of the study or withdrawal, whichever comes first.
Incidence rate of laboratory confirmed or probable symptomatic dengue infections	All symptomatic dengue infections (including laboratory-confirmed and probable cases) during the period.	Total person-years at risk*.
Incidence rate of probable symptomatic dengue infection	All probable symptomatic dengue infection	Total person-years at risk*.
Proportion of subjects with primary inapparent dengue infection	All dengue IgG positive cases at the considered visit	Total number of IgG negative subjects at the previous visit
Proportion of subjects with secondary symptomatic dengue infection	All symptomatic infection since the previous visit	Total number of IgG positive subjects at the previous visit
Seroprevalence of dengue infection	All dengue IgG positive cases	Total number of subjects tested or previously positive

* Time at risk: In analyses by season the time at risk is calculated as the time from the visit scheduled before the season until the first event during the season, the next scheduled visit or the subject's withdrawal, whichever comes first.

In the analyses of all seasons combined the time at risk is calculated as the time from enrolment until the first event, the end of the study or the subject's withdrawal, whichever comes first.

CIs for incidence rates and proportions will account for clustering of observations within households for the analyses by centre and also the stratification by centres for the overall analyses. Details of the methods will be described in the SAP.

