5.7.1.1. Suspected symptomatic dengue case (Amended 16 October 2017)

Febrile illness with body temperature $\geq 38^{\circ}\text{C}$ measured (by any route) on at least two consecutive days and less than 14 days with or without the presence of other dengue symptoms or signs, without an obvious aetiology unrelated to dengue, based on investigator’s judgement.

Although subjects are asked to come to a study hospital if fever (body temperature $\geq 38^{\circ}\text{C}$) *is* sustained for two consecutive days, a subject *could* present on the first day of fever. In this case the physician may still consider the subject as a suspected dengue case based on medical judgement and collect a blood sample for laboratory diagnosis.

Subjects should be examined at the health care facility during the 5 days following fever onset, as this is a requirement for RT-qPCR diagnosis of dengue infection and serotype identification.

However, subjects presenting until 30th (included) day of fever onset will be considered for investigation. After the 30th day, subjects will not be considered as suspected dengue cases.

A suspected dengue case presenting at the health care facility within 5 days following the onset of fever will be defined as an ‘early presenter’.

Subjects presenting for care *between sixth and 30th day* of fever onset will be defined as ‘late presenters’.

An example of other signs and symptoms of dengue, associated with fever, include but are not limited to: fatigue, headache, pain behind the eyes, abdominal pain, nausea, vomiting, muscle ache, joint ache, diffuse rash on the trunk, abnormal sensitivity to light (photophobia) and itching of skin (pruritus).

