5.7.1.2. Laboratory-confirmed symptomatic dengue case (Amended 16 October 2017)

Early presenter:

At least one of the following findings must be met for a laboratory-confirmed dengue case:

- Dengue virus identification through RT-qPCR on the acute serum sample
- Dengue virus NS1 positive on acute serum sample through ELISA.
- Anti-dengue IgM seroconversion between acute and convalescent serum samples through ELISA.

Late presenter:

- ***Anti-dengue IgM seroconversion between acute and convalescent serum samples through ELISA.***

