7.2. Analysis of primary and secondary endpoints

7.2.1. Analysis as planned per protocol

The following analyses will be performed overall and by DENV type, study site, gender and age-group previous dengue exposure (Yes = DENV IgG antibodies at previous visit and No = no DENV IgG antibodies at previous visit):

- Incidence rate of *laboratory-confirmed symptomatic dengue infection* with 95% CI for each season separately: the numerator will be the number of subjects with lab-confirmed symptomatic dengue infection during the season (between the visits scheduled before and after the season). The denominator will be the total person-years at risk, i.e. from the visit scheduled before the season until the first RT-qPCR confirmed symptomatic dengue infection during the season, the next scheduled visit or the subject's withdrawal, whichever comes first.

- Incidence rate of *laboratory-confirmed symptomatic dengue infection* with 95% CI all seasons combined: the numerator will be the number of subjects with lab-confirmed symptomatic dengue infection during the study period. The denominator will be the total person-years at risk, i.e. from enrolment until the first RT-qPCR confirmed symptomatic dengue infection, the end of the study or the subject's withdrawal, whichever comes first.

The following analyses will be performed by study site, gender and age-group previous dengue exposure (primary or secondary):

- Incidence rate of *laboratory confirmed or probable symptomatic dengue infections* with 95% CI for each season separately and overall. The numerator will be the number of subjects with symptomatic dengue infection (including laboratory-confirmed and probable cases) during the period. The denominator will be the total person-years at risk.
- Incidence rate of *probable symptomatic dengue infection* with 95% CI for each season separately and overall. The numerator will be the number of subjects with probable symptomatic dengue infection. The denominator will be the total person-years at risk.

The following analyses will be performed by study site, gender and age-group:

- The proportion of subjects with *primary inapparent dengue infection* at each subsequent scheduled visit (not at enrolment) with 95% CI will be calculated as the number of dengue IgG positive cases and at the visit divided by the total number of subjects IgG negative at the previous visit.

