7.4. Analysis of incidences

The analyses will be performed on the ATP cohort.

The following analyses will be performed overall and by DENV type:

- Incidence rate (expressed as number of cases/1000 person-years) of laboratory-confirmed symptomatic dengue infection with 95% CI (refer to Section [12.1](#) for the methodology for computing 95%CI) for each dengue season separately: the numerator will be the total number of laboratory-confirmed symptomatic dengue infections during the specific season (first of such event per subject during the specific season, using the date of first symptom onset). The denominator will be the total person-years at risk during the specific season, i.e. from the start of the specific season* until the first laboratory-confirmed symptomatic dengue infection during the

specific season, the end of the specific season or the subject's withdrawal, whichever comes first. Subjects withdrawn before the start of the specific season will not be included in the denominator.

- **From Visit 1 for subjects enrolled during the specific season. Subjects diagnosed with dengue between the start of the specific season up to before Visit 1 will not be included in the denominator for the specific season.*
- Incidence rate (expressed as number of cases/1000 person-years) of laboratory-confirmed symptomatic dengue infection with 95% CI for all dengue seasons combined: the numerator and denominator will be respectively the sum of each numerator and denominator used in the computation of incidence rates by season.

The following analyses will be performed overall, by study site, gender, age category and previous dengue exposure (primary or secondary):

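### The primary rate counts any laboratory-confirmed case but stops person-time only at an RT-qPCR-confirmed case; the downward bias is small at the planned incidence, but the rule is wrong as written

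*Protocol*

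**What the plan says.** **Case definition.** Protocol 5.7.1.2 accepts several routes to confirmation in early presenters: "At least one of the following findings must be met for a laboratory-confirmed dengue case", the findings being RT-qPCR, NS1 and IgM seroconversion. Late presenters can be confirmed only by IgM seroconversion. Protocol 5.7.1.1 asks for examination within five days of fever onset, "as this is a requirement for RT-qPCR diagnosis of dengue infection and serotype identification". The assay table in SAP Amendment 1 section 7 lists RT-qPCR as not performed in late presenters.

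**Numerator.** In the text of protocol 8.5.2, "the numerator will be the number of subjects with lab-confirmed symptomatic dengue infection during the season". Table 16 in the same section has "All confirmed acute cases during the study period" for the all-seasons rate, which reads as cases rather than subjects.

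**Denominator.** By season, time runs "until the first RT-qPCR confirmed symptomatic dengue infection during the season", the next scheduled visit or withdrawal. For all seasons combined it runs "from enrolment until the first RT-qPCR confirmed symptomatic dengue infection, the end of the study" or withdrawal. For the confirmed-or-probable and probable rates, the footnote to Table 16 stops time at the first event, which matches their numerators.

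**SAP versions.** The June 2019 SAP, section 7.4, measures time "from the start of the specific season* until the first laboratory-confirmed symptomatic dengue infection" and counts one such event per subject per season. The November 2017 interim SAP, section 8.4, does the same. Amendment 1 (October 2019), section 7.2.1 and Table 1, returns to the protocol rule: "from enrolment until the first RT-qPCR confirmed symptomatic dengue infection". Its section 7.2.2.1 then drops the by-season analyses and fits a Poisson model to the number of dengue events, glossed as all cases, with subject-months as offset. Section 11.3.3 defines follow-up days within a month. Neither section says when a case's subject-months end.

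**The concern.** A rate based on first events needs its clock to stop at the event it counts. Here a subject confirmed by NS1 or IgM alone has already supplied the one count that the text allows, yet goes on adding person-time. No late-presenter case can ever stop the clock. Numerator and denominator therefore describe different events in the study's primary estimate, which is wanted for checking attack-rate assumptions in later efficacy trials.

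Reproducibility is also at stake. The protocol text counts subjects, Table 16 counts cases, and the Amendment 1 model counts events without defining all cases. Two programmers could follow the current documents and obtain different denominators, and different counts, for the same primary rate.

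**Working it through.** **Inputs**
- Expected incidence: about 10 per 1000 person-years (protocol 8.2.1). Table 15 spans 3 to 15 per 1000.
- Annual drop-out: 15 to 20% (protocol 8.2.1). The 15% figure reproduces Table 15, giving a hazard μ = −ln 0.85 = 0.1625.
- Design effect: 1 + (3 − 1) × 0.4 = 1.8 (protocol 8.2.2).
- RT-qPCR share s of laboratory-confirmed cases: not given. Amendment 1 reports 10 RT-qPCR-confirmed cases but no total, so s is varied over its whole range, 0 to 1.

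**Reproducing the plan's figures.** Person-years for 3600 subjects over one year: 3600 × 0.15 / 0.1625 = 3322.7 (with unrounded μ), as in Table 15. Confidence interval at 9 per 1000: 9 ± 1000 × 1.96 × √(0.009 × 1.8 / 3322.7) = 9 ± 4.3, or [4.7; 13.3], as stated in 8.2.3. With the 8611.3 person-years printed for the four-year row, the half-width is 2.7 and the interval [6.3; 11.7], also as stated.

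**Size of the mismatch.** Assume a constant case hazard L and drop-out hazard μ, and count the first confirmed case per subject over T years. Per subject enrolled:
- matched time: C = (1 − exp(−(L + μ)T)) / (L + μ);
- time if no case stops the clock: A = (1 − exp(−μT)) / μ;
- time under the written rule: P = (1 − s)A + sC;
- denominator excess: P/C − 1 = (1 − s)(A/C − 1);
- rate obtained: L × C/P.

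At 9 per 1000:
- T = 1: C = 0.91894, A = 0.92297. With s = 0 the excess is 0.44% and the rate 8.96. With s = 0.5 it is 0.22% and 8.98. With s = 1 there is no bias.
- T = 4: C = 2.89444, A = 2.94116. With s = 0 the excess is 1.6% and the rate 8.86. With s = 0.5 it is 0.8% and 8.93.

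Largest excess (s = 0) at other incidences:

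| True rate per 1000 | One season | Four years |
|---|---|---|
| 3 | 0.15% | 0.5% |
| 9 | 0.44% | 1.6% |
| 15 | 0.73% | 2.7% |
| 50 | 2.5% | 9.2% |
| 100 | 4.9% | 18.8% |

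The last two rows lie outside the planned range. They are assumptions that show how the error grows with transmission.

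**Against the planned precision.** At 9 per 1000 the shortfall is at most 9.00 − 8.96 = 0.04 per season against a half-width of 4.3, and 9.00 − 8.86 = 0.14 over four years against 2.7.

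**Is the rule replaced elsewhere in Amendment 1?** Section 10 says that all changes are in the additional-considerations sections, 7.4 and section 1. None of these mentions the stopping rule, so the RT-qPCR wording remains the only written stop for the primary rate.

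**The case against.** The strongest reply is that section 7.2.1 of Amendment 1 only records the protocol's plan. The by-season analyses are gone, and the operative model in 7.2.2.1 applies no RT-qPCR censoring. If that model counts every case over all subject-months, it gives a coherent rate without this bias. The four-year figures fit the protocol's enrolment-to-first-event definition better than Amendment 1, which averages modelled monthly rates and, by section 7, had shorter coverage at Salvador, Natal and Campinas.

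Much of this stands. It limits the reach of the four-year figures and means that editing 7.2.1 alone would not settle the matter. It does not remove the defect: the model's all cases is undefined, no section says whether subject-months end at a case, and the one stop that is written is the wrong one.

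Three stronger readings are tempting and unsupported:
- *That time keeps accruing after most events.* This needs more than 20 confirmed cases in total, given 10 by RT-qPCR; the total is not reported.
- *That the bias is always downward.* This holds when each subject's first case is counted. If repeat cases count, they can raise the rate, and time after a case is legitimate time at risk.
- *That the error is material, say 7 to 11% over four years.* Errors of that order need an incidence near 5% per year, against a planned 0.3 to 1.5%. Amendment 1 itself reports few dengue episodes.

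**Conclusion.** The numerator and denominator events of the primary rate do not match in protocol 8.5.2 and Table 16. Amendment 1 repeats the mismatch after two SAP versions had avoided it. When the first case per subject is counted, the rate is biased downward. At 9 per 1000 the denominator excess is 0 to 0.4% per season and 0 to 1.6% over four years; at 15 per 1000 the upper limits are 0.7% and 2.7%. These figures rest on constant hazards, 15% annual drop-out and an unknown RT-qPCR share taken over 0 to 100%.

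The bias is minor in size, well inside the planned confidence intervals, and would be larger in a high-transmission site or year. The rule is still wrong as written, and the primary denominator cannot be reproduced from the current SAP.

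**What to change.** - In protocol 8.5.2 and Table 16, replace *first RT-qPCR confirmed* by *first laboratory-confirmed* in both primary rates, and make the Table 16 numerators count subjects, as the text does.
- Record this as a change in SAP 7.2.2.1 and 11.3.3, so that 7.2.1 can stay as the record of the protocol's plan. State there that, for the primary rate, the first laboratory-confirmed event per subject per calendar year is counted, and that the subject-months in the offset stop at that event for that year.
- Define all cases in the model description accordingly.

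The cost is a few sentences and one censoring date in the program. No new data are needed. Compared with the RT-qPCR stop, the first-case rates would rise slightly or stay the same.

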8.5.3. Analysis of symptoms and spectrum of dengue disease

The clinical characteristics of symptomatic dengue infection (symptoms, hospitalizations, severity) will be presented.

8.5.4. Analysis of tertiary objectives (Amended 16 October 2017)

Analysis of tertiary objectives is optional and may or may not be performed. If these analyses are performed, they will be conducted by the Research and Development Department. Statistical methods for tertiary objectives will be described in the SAP.

The neutralization assay, if performed, will only be done on blood samples from a subset of subjects. YF virus antibody testing will be performed retrospectively, for subjects in YF endemic region and who was tested positive for dengue.

Analysis of risk factors for symptomatic dengue

Poisson regression models will be used for exploring the risk factors (e.g. region, age and gender, etc.) for symptomatic dengue. The analyses will account for clustering of observations within households for the analyses by centre and also the stratification by centres for the overall analyses.

Incidence rates of symptomatic Zika infections

The following analyses will be performed by study site, gender and age-group, previous dengue exposure and previous Zika infection:

- *Incidence rate of laboratory-confirmed or probable symptomatic Zika infection with 95% CI for each season separately: the numerator will be the number of subjects with lab-confirmed or probable symptomatic Zika infection during the season (between the visits scheduled before and after the season). The denominator will be the total person-years at risk, i.e. from the visit scheduled before the season until the first lab-confirmed or probable symptomatic Zika infection during the season, the next scheduled visit or the subject's withdrawal, whichever comes first.*
- *Incidence rate of laboratory-confirmed or probable symptomatic Zika infection with 95% CI all seasons combined: the numerator will be the number of subjects with lab-confirmed or probable symptomatic Zika infection during the study Zika follow-up period. The denominator will be the total person-years at risk, i.e. from start of the study Zika follow-up period until the first lab-confirmed or probable symptomatic Zika infection, the end of the study or the subject's withdrawal, whichever comes first.*

Incidence rates of symptomatic chikungunya infections

The following analyses will be performed by study site, gender and age-group, previous dengue exposure and previous chikungunya infection:

- *Incidence rate of laboratory-confirmed or probable symptomatic chikungunya infection with 95% CI for each season separately: the numerator will be the number of subjects with lab-confirmed or probable symptomatic chikungunya infection during the season (between the visits scheduled before and after the season). The denominator will be the total person-years at risk, i.e. from the visit scheduled before the season until the first lab-confirmed or probable symptomatic chikungunya infection during the season, the next scheduled visit or the subject's withdrawal, whichever comes first.*
- *Incidence rate of laboratory-confirmed or probable symptomatic chikungunya infection with 95% CI all seasons combined: the numerator will be the number of subjects with lab-confirmed or probable symptomatic chikungunya infection during the study chikungunya follow-up period. The denominator will be the total person-years at risk, i.e. from start of the study chikungunya follow-up period until the first lab-confirmed or probable symptomatic chikungunya infection, the end of the study or the subject's withdrawal, whichever comes first.*

Analysis for Zika and chikungunya viruses in suspected dengue cases

The proportions and associated exact 2-sided 95% confidence intervals (CI) of the Zika and chikungunya viruses in suspected dengue cases will be summarized.

Analysis for seroprevalence of antibody titers against Zika and chikungunya viruses at selected timepoints

Seroprevalence at each selected timepoint will be calculated as a proportion i.e. the number of seropositive samples at each selected timepoint over the total number of samples with antibody results. An exact 95% CI will be computed.

